9.5. Laboratory Evaluations

[figure not shown]
Non-fasting samples will be collected for serum chemistry, hematology, coagulation (INR), and urinalysis at Screening, Week 12, and Week 36/End of Study. In addition, for women of child bearing potential, a pregnancy test will be evaluated at Screening, Baseline, Week 12, and Week 36/End of Study. Blood samples for antibody testing are collected at Screening, Week 6, Week 12, and Week 36/End of Study. The hematology tests that will be collected are: Hemoglobin, Hematocrit, Leukocyte count (total), Leukocyte count (differential), Red blood cell count, and Platelet count. Serum chemistry tests that will be collected are: Sodium, Potassium, Chloride, Carbon dioxide (Bicarbonate), Calcium, Albumin, Glucose, Total bilirubin, Alanine aminotransferase, Aspartate aminotransferase, Alkaline phosphatase, Blood urea nitrogen, and Creatinine. Urinalysis tests that will be collected are: Specific gravity, pH, Glucose, Protein, Blood, Bilirubin, and Ketones. Additional tests that may be collected are: Prothrombin time, urine pregnancy for women of childbearing potential, serum pregnancy test at end of study if urine pregnancy test is positive, and [REDACTED] Summary tables and listings will report laboratory results using Système International (SI) units.

Summary statistics for observed values and changes from baseline will be provided for chemistry, hematology, coagulation, [REDACTED] at each visit by treatment. Summary statistics for observed urinalysis values will be provided at each visit by treatment.

Shift tables will be provided for shift from Baseline to Week 12 and shift from Baseline to Week 36/End of Study. Shift tables will be based on normal ranges and results reported as low, normal, or high. For urinalysis values, results will be reported as normal or abnormal.

A listing will be provided for all laboratory values at all visits. A listing of all out-of-range or clinically significant laboratory test results at any evaluation will be provided. Determination of clinical significance for all out-of-range laboratory values were to be made by each investigator and will be included in the listing.

This document is confidential.

This document is confidential.

9.7. Vital Signs

Vital signs include weight, body temperature, respiration rate, sitting radial pulse rate, and sitting systolic and diastolic blood pressure and are collected at Screening, Baseline, Week 2, Week 4, Week 6, Week 8, Week 12, Week 16, Week 20, Week 24, Week 28, Week 32, and Week 36/End of Study. Height is collected at the Screening visit only. Body Mass Index (BMI) will be computed using the weight at each visit and height at Screening: $BMI = \text{weight (kg)} / \text{height (m)}^2$.

Vital signs will be summarized by treatment and visit. All vital signs will be included in a listing.

9.8. ECG

A standard 12-lead ECG will be performed after the subject has rested quietly in the supine position at Screening, Week 12, and Week 36/End of Study. ECG data will be submitted to a central reader for review.

A summary of the overall ECG interpretation will be provided by treatment and visit. Summary statistics for ECG interval data will be provided by treatment and visit. The number and percentage of subjects in each of the following QTcF categories will be provided by visit and any post-treatment visit:

- $QTcF > 450$ msec for males or > 470 msec for females
- $QTcF > 480$ msec
- $QTcF > 500$ msec
- Increase from baseline $QTcF \geq 30$ msec
- Increase from baseline $QTcF \geq 60$ msec

If the ECG is repeated more than once at any timepoint, average values will be used for the summary. All ECG results will be included in a listing

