9.10. Pulmonary Function Test

[figure not shown]
Pulmonary function will be recorded using spirometry. Parameters measured are the forced vital capacity (FVC), which is the total volume of air exhaled during forced expiration, and the forced expiratory volume in the first second of exhalation (FEV₁). Spirometry results are collected at Baseline, Week 6, Week 12, and Week 36/End of Study, however, if there is a post-treatment decline in FVC \geq 20%, continue to monitor FEV₁ and FVC at all subsequent study visits. The FVC and FEV₁ results and changes from baseline will be summarized by treatment and visit. All data will be provided in a listing. Note, spirometry was discontinued 20 March 2020 to reduce the risk of possible spread of infection due to COVID-19.

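### Absolute QTcF counts do not separate new cases from those already over the cut-off before dosing, and no change from baseline is specified for vital signs or ECG intervals

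*SAP*

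**What the plan says.** SAP 9.8 schedules the ECG at Screening, Week 12 and Week 36/End of Study. By the baseline definition in SAP 6.2 (last non-missing value before the dose), the Screening ECG is normally the baseline. For QTcF, "The number and percentage of subjects in each of the following QTcF categories will be provided by visit and any post-treatment visit". Five categories follow: above 450 msec for men or 470 for women, above 480, above 500, and increases from baseline of at least 30 and at least 60 msec. None of the three absolute categories is restricted to subjects below the cut-off before dosing. For the intervals as continuous measures, "Summary statistics for ECG interval data will be provided by treatment and visit". Overall ECG interpretation is likewise summarized by treatment and visit.

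SAP 9.7 says "Vital signs will be summarized by treatment and visit" and mentions no change from baseline.

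Two neighbouring sections go further. SAP 9.5: "Summary statistics for observed values and changes from baseline will be provided for chemistry, hematology, coagulation", with shift tables to Week 12 and to Week 36/End of Study. SAP 9.10, for FVC and FEV1: "results and changes from baseline will be summarized by treatment and visit".

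**The concern.** Comparing safety across three doses and placebo is part of the primary objective (SAP 3.1). A count of subjects over an absolute QTcF limit at any post-treatment visit mixes two things: prolongation that arose after the injection and prolongation that was there before it. Only the first bears on the drug. In small arms, a chance difference in how many subjects entered with a long QTcF carries straight into the post-treatment count.

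Vital signs and ECG intervals raise a related point. Means of observed values by visit compare arms through the full between-subject spread, and they do not follow the same person from before to after. The composition of the later visits also shifts: before the COVID-19 hold, subjects leave after Week 12 according to response, and those enrolled after the hold stop at Week 12 (Protocol 3.6). A mean at Week 24 therefore describes a different group from the mean at baseline.

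**Working it through.** The plan states no figure on this point, so there is none to reproduce. The first step is a reading of the text. The others are illustrations on assumed inputs.

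**1. Text, side by side**

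| Measure | Change from baseline specified? | Shift or new-case table specified? |
|---|---|---|
| Laboratory values (9.5) | Yes, for chemistry, hematology and coagulation | Yes |
| FVC, FEV1 (9.10) | Yes | No |
| QTcF categories (9.8) | Yes, at least 30 and at least 60 msec | No, for the three absolute cut-offs |
| ECG intervals (9.8) | No | No |
| Overall ECG interpretation (9.8) | Not applicable | No |
| Vital signs (9.7) | No | No |

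SAP 6.2 defines change from baseline but does not require it for any variable. The SAP names change where it intends it, so silence in 9.7 and 9.8 is best read as no change summary specified.

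**2. How many QTcF cases could be pre-existing**

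Assumed: QTcF mean 415 to 425 msec, between-subject SD 18 to 20, within-subject SD 9 to 10, two post-dose ECGs, no drug effect, half the subjects women with the same mean as men, 32 per arm. The total of about 128 is in SAP 3.4; equal allocation is an assumption.

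- Prevalence before dosing = ½·P(Z > (450 − mean)/SD) + ½·P(Z > (470 − mean)/SD), where SD is the total SD, √(between² + within²).
- Example, upper end: SD = √(20² + 10²) = 22.4. (450 − 425)/22.4 = 1.12 gives 13.2%; (470 − 425)/22.4 = 2.01 gives 2.2%. The average is 7.7%, or 2.5 subjects in 32.
- Over the whole grid: prevalence 2.2 to 7.7%, or 0.7 to 2.5 subjects per arm.
- Share of subjects over 450/470 at any post-treatment ECG who were already over before dosing, by simulation: 38 to 53%.
- Expected pre-existing cases per arm: 0.02 to 0.22 above 480 msec, and at most about 0.01 above 500 msec.

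A wider check used one post-dose reading, a single 450 msec cut-off, mean 410 to 430, SD 20 and pre/post correlation 0.6 to 0.8. The already-over share ranged from about 25 to 62%.

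**3. Chance imbalance before dosing**

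With two independent binomial counts of size 32 at prevalence 2.2 to 7.7%, two given arms differ by three or more pre-existing cases in about 4 to 23% of trials. A single 450 msec limit for both sexes, at prevalence 5 to 15%, would give 14 to 38%, but that is not the SAP's category.

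**4. Precision of an arm difference: observed values or change**

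Half-width of the 95% interval = 1.99·SD·√(2/32) = 0.4975·SD. The SD of a change is SD·√(2(1 − r)), where r is the pre/post correlation. All SDs and correlations are assumed.

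| Measure | SD | r | Observed | Change |
|---|---|---|---|---|
| Weight (kg) | 18 | 0.97–0.99 | 9.0 | 2.2–1.3 |
| QTcF (msec) | 22 | 0.6–0.8 | 10.9 | 9.8–6.9 |
| Systolic BP (mmHg) | 17 | 0.5–0.7 | 8.5 | 8.5–6.6 |

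The factor √(2(1 − r)) is below 1 only when r exceeds 0.5. For systolic pressure at r = 0.4, change is worse: 17·√1.2 = 18.6, half-width 9.3 mmHg.

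**The case against.** A reader might infer that the ECG tables ignore the baseline altogether. They do not: two of the five QTcF categories are increases from baseline, given by visit and at any post-treatment visit. A reader might also infer that a dose effect would be hidden. The documents do not support that either:

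- Tables are by visit and include pre-dose visits, so the pre-dose count and mean per arm should be visible.
- Every value is listed.
- Treatment is randomized.
- Protocol 6.2.2.1 requires clinically significant post-treatment changes, with vital signs and ECG named, to be reported as adverse events. These then enter the treatment-emergent tables of SAP 9.3.
- A data monitoring committee reviews the accumulating safety data.

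The quantities are all assumed, pre-existing cases barely matter for the two higher QTcF limits, and change gains nothing for a measure with r at or below 0.5. Change scores at late visits still describe only the subjects who remain, so they do not cure response-driven attrition.

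All of this stands as a limit on the size of the point. It does not remove the point. Pre-dose counts by arm are marginal totals: two subjects over at Screening and two over later could be the same two people or four different ones, and no specified table says which. The two increase categories cover QTcF alone and do not show whether a subject above 480 or 500 msec is newly so. Parts of the SAP are redacted and the table shells are not visible, so they may already contain more than the text says.

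**Conclusion.** The gap is real and small. SAP 9.8 does not separate new from pre-existing cases in its three absolute QTcF categories. SAP 9.7 and 9.8 specify no change from baseline for vital signs or ECG intervals and no shift for ECG interpretation, which is less than the same SAP provides in 9.5 and 9.10.

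The new-case count matters mainly for the 450/470 category, where perhaps two in five to one in two of the post-dose cases could be pre-existing. Change summaries help clearly for weight, modestly for QTcF, and little or not at all for systolic pressure near r = 0.5. These sizes rest on assumed means, SDs, correlations, sex mix and 32 per arm, because the documents give none of them. No endpoint, test or error rate is affected, only descriptive safety tables. The case for acting is that the improvement is nearly free.

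**What to change.** - **SAP 9.8, QTcF:** keep the existing counts. Beside each absolute category, report new cases among subjects at or below that cut-off at baseline, with that group as the denominator. A shift from baseline category to worst post-dose category would do equally well.
- **SAP 9.8, other ECG results:** add change-from-baseline summaries by visit for the ECG intervals, and a shift from baseline for overall interpretation.
- **SAP 9.7:** add change from baseline by visit for each vital sign, computed in subjects with both readings and with the number shown. State that late-visit summaries describe only subjects still in follow-up.

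The cost is a few lines of SAP text and revised table shells. The pre-dose readings are already collected, so no visit, procedure or data item is added.

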9.9. Physical [REDACTED]

Physical [REDACTED] results are collected at Screening, Baseline, Week 2, Week 4, Week 6, Week 8, Week 12, Week 16, Week 20, Week 24, Week 28, Week 32, and Week 36/End of Study. A complete physical examination is performed at Screening and Baseline. At post-treatment visits, the physical examination may be abbreviated. Results will be summarized by treatment and visit. All data will be provided in a listing.

[figure not shown]
This document is confidential.

9.10. Pulmonary Function Test

[figure not shown]
Pulmonary function will be recorded using spirometry. Parameters measured are the forced vital capacity (FVC), which is the total volume of air exhaled during forced expiration, and the forced expiratory volume in the first second of exhalation (FEV₁). Spirometry results are collected at Baseline, Week 6, Week 12, and Week 36/End of Study, however, if there is a post-treatment decline in FVC \geq 20%, continue to monitor FEV₁ and FVC at all subsequent study visits. The FVC and FEV₁ results and changes from baseline will be summarized by treatment and visit. All data will be provided in a listing. Note, spirometry was discontinued 20 March 2020 to reduce the risk of possible spread of infection due to COVID-19.

9.11. Columbia-Suicide Severity Rating Scale (C-SSRS)

[figure not shown]
The C-SSRS will be collected at screening and all visits. The number and percentage of subjects in each category of the suicidal ideation items will be summarized by visit and treatment. All C-SSRS information will be provided in a listing.

[figure not shown]
This document is confidential.

[figure not shown]
This document is confidential.

This document is confidential.

This document is confidential.

This document is confidential.

[figure not shown]
This document is confidential.

14. Quality Control

[figure not shown]
SAS programs are developed to produce output such as analysis data sets, summary tables, data listings, figures or statistical analyses. An overview of the development of programs is detailed in Syneos Health Standard Operating Procedure (SOP) Developing Statistical Programs (3907).

Syneos Health SOPs Developing Statistical Programs (3907) and Quality Deliveries (SDTM, ADaM, TLF) (3908) describes the quality control procedures that are performed for all SAS programs and output. Quality control is defined here as the operational techniques and activities undertaken to verify that the SAS programs produce the output by checking for their logic, efficiency and commenting and by review of the produced output."

[figure not shown]
This document is confidential.

[figure not shown]
This document is confidential.

[figure not shown]
This document is confidential.

[figure not shown]
This document is confidential.

[figure not shown]
This document is confidential.

This document is confidential.

[figure not shown]
This document is confidential.

[figure not shown]
This document is confidential.

[figure not shown]
This document is confidential.

[figure not shown]
This document is confidential.

[figure not shown]
This document is confidential.

This document is confidential.

This document is confidential.

This document is confidential.
